9. PRIOR AND CONCOMITANT MEDICATION

All medications will be coded using the World Health Organization – Drug Dictionary (WHO-DD) Version 01SEP2016 categorized by anatomical therapeutic class (ATC) and preferred term. Medications/therapies/procedures will be further categorized as ocular or non-ocular by the investigator based on the indication for which the medication/therapy/procedure was used.

Prior medication/therapy/procedure is defined as any medication/therapy/procedure with a start date prior to the date of the first dose of investigational product.

Concomitant medication/therapy is defined as any medication/therapy with a start date prior to the date of the first dose of investigational product and continuing after the first dose of investigational product or with a start date between the dates of the first and last doses of investigational product, inclusively. Concomitant procedure is defined as any procedure with a start date between the dates of the first and last doses of investigational product, inclusively. Any medication/therapy/procedure with a start date after the date of the last dose of investigational product will not be considered a concomitant medication/therapy/procedure.

Both prior and concomitant medication usage will be summarized by the number and proportion of subjects receiving each medication within each ATC and each preferred term by treatment group and overall for the Safety Population. Medications can be counted both as prior and concomitant medication. Multiple medication usage by a subject in the same category will be counted only once.

Ocular and non-ocular medications will be summarized separately.

All prior and concomitant medication will be listed. Prior and concomitant therapy/procedure will not be summarized, but will be listed. Imputed dates (see Section 18.6 for imputation rules) will be marked in the listings.

Medication/therapy/procedure with a start date after the date of the last dose of investigational product will also be listed.

10. EFFICACY ANALYSES

All efficacy analyses will be based on the mITT unless stated otherwise. Baseline for all efficacy analyses is defined as the value for the efficacy assessment at Visit 1.

All statistical tests will be 2-sided hypothesis tests performed at the 4.99% level of significance for main effects. All confidence intervals (CIs) will be 2-sided 95% CI, unless stated otherwise.

All efficacy analyses will be conducted according to the treatment assigned.

Multiplicity adjustments will be done on the primary and key secondary efficacy endpoints testing as described in Section 2.6.

Missing post-baseline efficacy assessments will be imputed using LOCF from post-baseline values and all efficacy statistical inference will be made based on analyses using LOCF, unless stated otherwise. If a subject has no post-baseline efficacy assessment then no LOCF will be done for that efficacy assessment for the subject. In other words, the subject's Visit 3 (Day 5) data will remain missing which means the subject will be excluded from the primary analysis in mITT and sensitivity analysis in ITT for that efficacy assessment.

All efficacy endpoints will be listed in the ITT Population. The listing will include a flag to indicate whether the subject is in mITT.

10.1 Study Eye Designation

The study eye for analyses will be defined as follows, where an eligible eye is an eye with a score of at least 1 for both ocular conjunctival discharge and bulbar conjunctival redness at baseline:

- For subjects with both eyes eligible and both with a positive bacterial culture (presence of 1 or more bacterial species at or above pathological threshold) at baseline or both eyes eligible and both with a non-positive bacterial culture (absence of any bacterial species at or above pathological threshold) at baseline, the study eye will be the eye with the highest global clinical score (refer to Section 3.2) at baseline. If both eyes have the same global clinical score at baseline, then the study eye will be the right eye.
- For subjects with both eyes eligible with a positive bacterial culture in 1 eye at baseline, the baseline bacterial culture positive eye will be the study eye.
- For subjects with only 1 eligible eye, the eligible eye will be the study eye irrespective of its baseline bacterial culture result.

The study eye designation is summarized in the table below:

| Eligible Eye(s) | Bacterial Culture Results | Study Eye |
|-----------------|-------------------------------------|--|
| Both eyes | Both eyes positive | Highest global clinical score at Visit 1 (or right eye if scores are the same) |
| Both eyes | Both eyes negative | Highest global clinical score at Visit 1 (or right eye if scores are the same) |
| Both eyes | One eye positive | The bacterial culture positive eye at Visit 1 |
| One eye | Positive or negative for either eye | The eligible eye |

The eye other than the study eye is considered the fellow eye in all safety analyses.

10.2 Primary Efficacy Endpoint and Analysis

The primary efficacy endpoint is clinical resolution status (defined as absence [ie, a score of 0] of bulbar conjunctival injection and ocular conjunctival discharge) in the study eye at Visit 3 (Day 5) between SHP640 and placebo.

The null hypothesis to be tested is that there is no difference in proportion of subjects with clinical resolution in the study eye between SHP640 ophthalmic suspension and placebo with the alternative of the non-zero difference in the proportion with clinical resolution between them. The proportion of subjects with clinical resolution will be compared between SHP640 and placebo groups using two-sided Fisher's Exact test at two-sided 4.99% level of significance. Missing data will be imputed based on post baseline LOCF for the determination of clinical resolution in the study eye at Visit 3 (Day 5). The primary basis of inference for this comparison will be based on the analysis conducted in mITT. Frequency and percent of subjects who reached/did not reach clinical resolution in the study eye at Visit 3 (Day 5) will be reported by treatment group along with the two-sided Fisher's Exact test p value for comparison between SHP640 and placebo. The two-sided 95% CI for response rate (exact CI for binominal proportion) in each treatment group as well as the estimated difference in response rates and corresponding two-sided 95% asymptotic CI for the difference will also be reported.

Example SAS code for conducting Fisher's exact test and generating the CIs is in Appendix [20.2.1](#).

10.3 Sensitivity Analyses for the Primary Efficacy Endpoint

ITT Population Analysis

A sensitivity analysis will be conducted by repeating the primary analysis using the ITT Population. Frequency and percent of subjects who reached/did not reach clinical resolution in the study eye at Visit 3 (Day 5) will be reported by treatment group along with the two-sided Fisher's Exact test p value for comparison between SHP640 and placebo. The two-sided 95% CI for response rate (exact CI for binominal proportion) in each treatment group as well as the estimated difference in response rates and corresponding two-sided 95% asymptotic CI for the difference will also be reported.

Missing Data Imputation

Method 1: Modified Worst Observation Carry Forward (WOCF)

The between-treatment group comparison (SHP640 versus placebo) for the primary efficacy endpoint will be performed using Fisher's Exact test on the mITT data set. Missing data will be imputed based on post baseline WOCF for the determination of clinical resolution in the study eye at Visit 3 (Day 5). For clinical resolution status, not reaching clinical resolution is considered worse than reaching clinical resolution. If a subject has no post-baseline efficacy assessment up to Visit 3 (Day 5), then his/her baseline efficacy assessment will be carried forward as the Visit 3 (Day 5) assessment.

Frequency and percent of subjects who reached/did not reach clinical resolution in the study eye at Visit 3 (Day 5) in the imputed data set will be reported by treatment group along with the two-sided Fisher's Exact test p value for comparison between SHP640 and placebo. The two-sided 95% CI for response rate (exact CI for binominal proportion) in each treatment group as well as the estimated difference in response rates and corresponding two-sided 95% asymptotic CI for the difference will also be reported.

Method 2: Multiple imputations

Multiple imputation (MI) methods will utilize the SAS procedures PROC MI and PROC

MIANALYZE in mITT. The MI procedure will first impute the global clinical score (GCS) at Visit 3 based on a regression model with treatment, age strata (< 6 years, 6 to <18 years and ≥18 years) as categorical independent variables and baseline GCS and GCS at Visit 2 as continuous independent variable assuming monotone missing pattern. In case the missing pattern is not monotone, Markov Chain Monte Carlo (MCMC) multiple imputation will be conducted first to impute enough data to produce a monotone missing data pattern. The MI procedure will generate 10 datasets with missing data imputed. The imputed GCS data will be rounded to integers and bounded to 0 to 7 during imputation so that the imputed values match the format of the observed values as well as existing range. Once the missing values are imputed and each dataset is created, clinical resolution status at Visit 3 will be derived based on the GCS scores at Visit 3. Binomial proportion for clinical resolution at Visit 3 in each treatment group, corresponding standard error (SE), the difference in the proportions between SHP640 and placebo and SE of the difference will be generated in each imputed data set and then appropriately pooled across the multiply imputed data sets using PROC MIANALYZE. The pooled binominal proportion point estimate in each treatment arm, the two-sided 95% CI for pooled proportion point estimate, the pooled point estimate of the difference between proportions in SHP640 and placebo, the corresponding p value and two-sided 95% CI will be reported.

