2.1 General Study Design

SHP640-303 is a global, multicenter, randomized, double-masked, parallel-group, placebo-controlled study designed to demonstrate the safety and efficacy of SHP640 ophthalmic suspension compared to placebo in treating bacterial conjunctivitis. In addition, an exploratory arm of povidone-iodine (PVP-I) 0.6% ophthalmic solution will be included.

Once screening and baseline assessments are complete and subjects are confirmed eligible to enroll in the study, subjects will be randomized, and investigational product (IP) will be administered on the same day (Day 1). The first dose will be administered by site staff on Day 1, and thereafter subjects will administer 1 drop in each eye 4 times a day (QID) for 7 days. Additional visits will occur on Days 3 (Visit 2), 5 (Visit 3), 8 (Visit 4), and 12 (Visit 5). All follow-up procedures will be conducted at Visit 5 (Day 12). The study will last up to 13 days.

Figure 1 provides the study design.

Figure 1: SHP640-303 Study Design

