10.5 Key Secondary Efficacy Endpoints and Analysis

The key secondary efficacy endpoint of this study is bacterial eradication status (defined as absence of all bacterial species present at or above pathological threshold at baseline) in the study eye at Visit 3 (Day 5) between SHP640 and placebo.

The null hypothesis to be tested is that there is no difference in proportion of subjects reaching bacterial eradication in the study eye at Visit 3 (Day 5) between SHP640 and placebo with the alternative hypothesis of non-zero difference in the proportion of responders between the two treatment groups.

In order to maintain the study-wide Type I error at 5% (two sided alpha of 0.0001 at IA and two sided alpha of 0.0499 at final analyses), the primary and key secondary hypotheses will be tested sequentially using two-sided Fisher's exact test with the primary efficacy endpoint being tested first and the key secondary efficacy endpoint being tested second. The hypothesis test for the key secondary efficacy endpoint will not be performed unless the hypothesis test for the primary efficacy endpoint is statistically significant.

Missing data will be imputed based on the post baseline LOCF for the determination of bacterial eradication status in the study eye at Visit 3 (Day 5). The primary basis of inference for the key secondary comparison will be based on the analysis conducted in mITT. Frequency and percent

of responders in the study eye at Visit 3 (Day 5) will be reported by treatment group along with the two-sided Fisher's Exact test p value for comparison between the two treatment groups. The two-sided 95% CI for response rate (exact CI for binominal proportion) in each treatment group as well as the estimated difference in response rates and corresponding two-sided 95% asymptotic CI for the difference will also be reported.

Sensitivity and exploratory analyses will also be conducted on key secondary efficacy endpoint using the same methods as described in Section 10.3 and 10.4 (i.e. modified WOCF imputation and multiple imputation as sensitivity analyses; adjusted Chi-square test and analysis based on CRF visits as exploratory analyses) except for the ITT population sensitivity analysis, which will not be conducted for bacterial eradication key secondary endpoint.

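### Modified WOCF (SAP 10.3 Method 1, reused in 10.5) repeats the primary LOCF value for subjects whose only assessment before a missing Visit 3 is Visit 2, so agreement between the two is weak evidence of robustness

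*SAP*

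**What the plan says.** **Primary rule.** SAP Section 10 states: "Missing post-baseline efficacy assessments will be imputed using LOCF from post-baseline values". Section 10.2 applies this to clinical resolution at Visit 3. For subjects with nothing to carry, Section 10 adds: "If a subject has no post-baseline efficacy assessment then no LOCF will be done for that efficacy assessment for the subject". The consequence is that "the subject will be excluded from the primary analysis in mITT and sensitivity analysis in ITT for that efficacy assessment".

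**Method 1.** SAP 10.3 replaces the last value by the worst: "Missing data will be imputed based on post baseline WOCF for the determination of clinical resolution in the study eye". It fixes the ordering, namely that "not reaching clinical resolution is considered worse than reaching clinical resolution". A subject with no post-baseline assessment up to Visit 3 has the baseline value carried forward instead.

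**Key secondary endpoint.** SAP 10.5 reuses the same methods for bacterial eradication ("modified WOCF imputation and multiple imputation as sensitivity analyses") and drops the ITT sensitivity analysis for that endpoint.

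**Schedule and mapping.** Post-baseline visits are on Days 3, 5, 8 and 12 (SAP 2.1). SAP 18.2 assigns assessments by date, with Days 3-4 for Visit 2 and Days 5-6 for Visit 3. Under SAP 18.4, assessments that fall in no window enter both LOCF and modified WOCF.

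**Method 2.** SAP 10.3 also plans multiple imputation of the Visit 3 global clinical score from treatment, age stratum, baseline score and Visit 2 score.

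**The concern.** A worst-observation analysis is normally read as the pessimistic counterpart of LOCF. Here the schedule leaves one planned value to carry, so for most subjects who have some early data but miss Visit 3 the two rules have nothing to disagree about. A subject clear on Day 3 and not seen on Day 5 or 6 counts as resolved under both.

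If the report shows Tables 14.2.1.1.1 (LOCF) and 14.2.1.2.1.2 (modified WOCF) agreeing, a reader will take that as support for the carry-forward assumption, although much of the agreement follows from the design. The untested assumption is the favourable one, that an eye clear on Day 3 stays clear. It would matter if loss after Day 3 differed between arms, for example through tolerability.

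**Working it through.** **1. The plan's own figure.** SAP 2.5 gives about 90% power with 216 per arm at 61% vs 45%. Exact enumeration of the two-sided Fisher test gives 89.9%, at alpha 0.05 and at 0.0499. The figure reproduces and is not in dispute; 216 per arm and these rates are used below.

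**2. Every possible history before a missing Visit 3** (R = resolved, N = not resolved). LOCF takes the last entry. Modified WOCF takes N if any entry is N, and baseline if there are none. Baseline is always N, because SAP 10.1 requires a score of at least 1 on both signs in an eligible eye.

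| Post-baseline history | LOCF | Modified WOCF | Same? |
|---|---|---|---|
| none | excluded | N | no |
| N | N | N | yes |
| R | R | R | yes |
| N, N | N | N | yes |
| N, R | R | N | no |
| R, N | N | N | yes |
| R, R | R | R | yes |

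With one assessment the rules agree in 2 of 2 histories. With two they differ in 1 of 4. A subject clear at every earlier assessment is R under both.

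**3. What the other planned analyses do with a subject clear at Day 3 and missing at Visit 3.**
- ITT analysis: same LOCF, so resolved.
- Multiple imputation: Visit 3 score drawn from a model containing treatment and Visit 2 score. The subject can be imputed as not resolved, but is assumed to behave like comparable observed subjects in the same arm.
- None counts the subject as a failure by rule.

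**4. How many subjects.** The documents give no Visit 3 missing rate. Assume 3-10% missing, with 15-35% of those clear at Day 3, among 2 × 216 = 432 subjects:
- low: 432 × 0.03 × 0.15 = 1.9
- high: 432 × 0.10 × 0.35 = 15.1

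**5. Illustration.** Assume 61% and 45% resolved among subjects observed at Visit 3, and 30% (SHP640) and 15% (placebo) resolved at Visit 2 among those with Visit 2 only. Counts are rounded. Each cell gives SHP640 vs placebo, the difference in percentage points and the Fisher p-value.

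| Missing at Visit 3 | LOCF | Modified WOCF | All missing = failure |
|---|---|---|---|
| 11 per arm, Visit 2 only | 128/216 vs 94/216; 15.7; 0.0015 | identical | 125/216 vs 92/216; 15.3; 0.0020 |
| 22 per arm, Visit 2 only | 125/216 vs 90/216; 16.2; 0.0011 | identical | 118/216 vs 87/216; 14.4; 0.0038 |
| 11 per arm Visit 2 only, plus 11 (SHP640) and 2 (placebo) with no post-baseline data | 121/205 vs 93/214; 15.6; 0.0017 | 121/216 vs 93/216; 13.0; 0.0093 | 118/216 vs 91/216; 12.5; 0.012 |
| 11 per arm Visit 2 only, plus 2 (SHP640) and 11 (placebo) with no post-baseline data | 127/214 vs 89/205; 15.9; 0.0013 | 127/216 vs 89/216; 17.6; 0.0004 | 124/216 vs 87/216; 17.1; 0.0005 |

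Row 1, first cell: 216 minus 11 leaves 205 observed; 205 × 0.61 ≈ 125, plus 11 × 0.30 ≈ 3, gives 128. For placebo, 205 × 0.45 ≈ 92, plus 11 × 0.15 ≈ 2, gives 94.

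In rows 1 and 2 only the failure analysis moves. In rows 3 and 4 Method 1 moves too, entirely through subjects with no post-baseline data. At these design rates no conclusion changes. A closer result could turn on one subject: 119/216 vs 97/216 gives p = 0.043, and 118/216 vs 97/216 gives p = 0.054.

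**The case against.** **Method 1 is not empty.** A reader might infer that it cannot test the LOCF handling at all. The documents do not support that. Subjects with no post-baseline data move from excluded to failure, and row 3 above shows that an early-dropout imbalance would appear there (15.6 to 13.0 points). The protocol can create such subjects: for baseline HSV-positive subjects who stop product, the follow-up listed in Protocol 4.4 covers safety assessments only, and the mITT definition does not remove them.

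**Some dropouts are observed.** Protocol Table 1 (footnote b) and Section 4.4 ask for Visit 5 evaluations at discontinuation where possible, including injection, discharge and swab. Under SAP 18.2 such a visit on Day 5 or 6 supplies the Visit 3 value, and one on Day 2 falls in no window and enters both imputations. How a second assessment inside the Day 3-4 window enters LOCF is less clear. The gap is therefore narrower than all discontinuations after Day 3; it lies mainly with subjects who have no exit assessment by Day 6. This stands.

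**Carry-forward is challenged elsewhere.** Method 2 does not carry the Visit 2 status forward, so the plan is not without a test of LOCF. This also stands; what is missing is a pessimistic one.

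**Power.** A reader might turn the affected counts into a loss of power. That would treat reclassification in an unpowered sensitivity analysis as a fall in the true response rate, and would put every case in one arm. The documents support neither step.

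**The alternative rule has limits.** Counting all missing as failures is not conservative for SHP640 if placebo has more missing data (row 4). It also fails a subject who was clear on Day 3 and again on Day 7 but missed the Day 5-6 window. These are reasons to report the missing counts alongside it.

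**Conclusion.** The point holds in a limited form. For subjects whose only assessment before a missing Visit 3 is Visit 2, Method 1 reproduces the primary value exactly, for clinical resolution and for eradication alike. Its real contribution is to count subjects with no post-baseline data as failures. Agreement with the primary analysis is thus weak evidence about the carry-forward assumption, and no planned analysis takes the pessimistic view of subjects clear at Day 3 who lack a Day 5-6 assessment.

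The effect on the result is unknown. The range of 2 to 15 of 432 subjects rests wholly on the assumed missing and Day 3 resolution rates, and in the worked examples the conclusion is unchanged. The primary test and its error control are unaffected. This is a worthwhile, inexpensive improvement to the sensitivity analyses and does not invalidate the plan.

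**What to change.** In SAP 10.3, and by reference in 10.5, add an analysis (or substitute it for Method 1) in which every mITT subject with missing Visit 3 status is counted as not resolved (not eradicated), whatever the Visit 2 status. Use the same Fisher test, difference and confidence interval. If it replaces Method 1, retitle Tables 14.2.1.2.1.2 and 14.2.1.2.2.1; if it is added, give it its own tables.

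This keeps every failure that Method 1 assigns and adds the Day 3-clear subjects. Report with it, by arm, the number with missing Visit 3 status, split into no post-baseline data, Visit 2 only and other, so that the direction of any bias can be judged.

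The cost is SAP wording, a derivation no harder than the present one and a small count table. The sensitivity estimate may come out slightly less favourable, and if placebo has more missing data it may come out more favourable to SHP640, which is why the counts are needed.

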2.5 Determination of Sample Size

The sample size was estimated for the primary comparison of SHP640 versus placebo on clinical resolution in the treatment of subjects with bacterial conjunctivitis in the study eye at Visit 3 (Day 5) using nQuery Advisor 7.0. Subjects will be randomized 3:1:3 to receive either SHP640, PVP-I, or placebo within each age stratum.

The primary efficacy endpoint is clinical resolution status (defined as absence [ie, a score of 0] of bulbar conjunctival injection and ocular conjunctival discharge) in the study eye at Visit 3 (Day 5) between SHP640 and placebo. The null hypothesis to be tested is that there is no difference in proportion of subjects with clinical resolution in the study eye between SHP640 ophthalmic suspension and placebo with the alternative of the non-zero difference in the proportion with clinical resolution between them.

A sample size of 504 subjects (216 subjects in each of the SHP640 and placebo groups, 72 in PVP-I group) will ensure ~90% power to compare the SHP640 and placebo treatment groups assuming 61% and 45% subjects with clinical resolution, respectively, using Fisher's Exact test at 2-sided 5% level of significance.

All efficacy analyses will be based on the modified Intent-to-Treat (mITT) population (refer to Section 4.4 for the definition of mITT) with post-baseline last observation carried forward (LOCF) for the subjects with missing clinical resolution status at Visit 3 (Day 5). To ensure 504 subjects in the mITT population, approximately 721 subjects will be randomized in this study (approximately 309 subjects in each of SHP640 and placebo groups; approximately 103 subjects in PVP-I group).

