18.3 Derived Efficacy Endpoints

Clinical resolution is defined as absence of bulbar conjunctival injection and ocular conjunctival discharge. Bulbar Conjunctival Injection will be assessed based on a 0-4 scale which uses pictures from the Validated Bulbar Redness (VBR) Scale. Ocular Conjunctival Discharge will be assessed based on a 0-3 scale. For both bulbar conjunctival injection and ocular conjunctival discharge, 0 score indicates normal or none and a higher score indicates a higher severity of the clinical sign. A 0 sum of bulbar conjunctival injection score and ocular conjunctival discharge score represents reaching clinical resolution. Any non 0 sum means not reaching clinical resolution. If either individual score is missing, clinical resolution status will be set to missing.

Bacterial eradication is defined as absence of all bacterial species present at or above pathological threshold at baseline (see Appendix 20.1 for pathological thresholds). Presence of at least one bacterial species that were at or above pathological threshold at baseline is considered not reaching bacterial eradication. If an eye has missing bacterial culture result at baseline, the eye will be assumed to be bacterial culture negative at baseline for determination of the study eye.

Global clinical score is defined as the sum of bulbar conjunctival injection score and ocular conjunctival discharge score. If either individual score is missing, global clinical score will be set to missing.

Modified clinical resolution is defined as a global clinical score of 0 or 1. All other scores are considered not reaching modified clinical resolution. If either individual score is missing, modified clinical resolution status will be set to missing.

Expanded clinical resolution is defined as a global clinical score of 0, 1, or 2 with neither bulbar conjunctival injection score nor ocular conjunctival discharge score having a score of 2. Otherwise, the subject is considered not reaching expanded clinical resolution. If either individual score is missing, expanded clinical resolution status will be set to missing.

Time to clinical resolution will be derived based upon assessments at Visits 2 (Day 3), 3 (Day 5), 4 (Day 8), and 5 (Day 12) in the study eye. Time to clinical resolution will equal to the study day corresponding to the visit when the subject first reaches clinical resolution in the study eye.

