20.2.2 Example SAS Code for Multiple Imputation

```
*First generate enough data to produce a monotone missing data pattern;
*Only include SHP640 and placebo arm in this imputation;
*MCMC does not work with class statement. Age has been converted to an
indicator variable;
*For <6 year old, age1=0 and age2=0, for 6-18 year old, age1=1 and age2=0,
for >18 year old, age1=0 and age2=1;
*all variables are rounded to integers. Age1, age2, and trt are bounded to 0
to 1, GCS_V2 and GCS_V3 are bounded to 0 to 7;
*Since bacterial eradication is a binary endpoint, the max bound for
bacterial eradication will be 1 instead of 7;
proc mi data = testIM3 seed =188 out = impOne NIMPUTE=10 round = 1 1 1 1 1 1
min = 0 0 0 0 0 0 max = 1 1 1 7 7 7;
mcmc impute = monotone;
var trt age1 age2 GCS_BASE GCS_V2 GCS_V3;
run;

*Full imputation based on a regression model assuming monotone missing
pattern;
*All missing treatment and age should have been imputed in MCMC step;
*Use an indicator variable for age to avoid warning message;
proc mi data = impOne seed = 321 out = impFinal NIMPUTE = 1 round = 1 1 1 1
1 1 min = 0 0 0 0 0 0 max = 1 1 1 7 7 7;
var trt age1 age2 GCS_BASE GCS_V2 GCS_V3;
monotone regression (GCS_V3 = trt age1 age2 GCS_BASE GCS_V2);
run;

*Convert GCS to clinical resolution;
data impFinal1;
set impFinal;
if (GCS_V3 = 0) then CS_V3 = 'Yes';
else CS_V3 = 'No';
run;

*Generate exact binomial proportions in imputed data set;
proc freq data = impFinal1;
tables CS_V3 / binomial (exact level='Yes') alpha=0.05;
by _IMPUTATION_ TREATMENT;
ods output BINOMIALPROP=prop;
run;

*create a dataset with estimated proportion of responders in each treatment
arm and their SE;
data prop_trt;
merge prop(where=(LABEL1='Proportion')) keep = _IMPUTATION_ TREATMENT NVALUE1
LABEL1 rename=(NVALUE1=proportion)
prop(where=(LABEL1='ASE')) keep = _IMPUTATION_ TREATMENT NVALUE1
LABEL1 rename=(NVALUE1=prop_se);
by IMPUTATION_ TREATMENT;
run;

*Combine proportion estimates;
proc mianalyze data = prop_trt;
modeleffects proportion;
stderr prop_se;
```

```
by treatment;  
run;
```

```
*compute estimates of the difference in proportions between SHP640 and  
placebo and the corresponding SE;
```

```
data trt_diff_640_pbo;  
merge prop_trt(where=(TREATMENT='SHP640')) rename=(PROPORTION=prop_640  
PROP_SE=prop_640_SE)  
prop_trt(where=(TREATMENT='Placebo')) rename=(PROPORTION=prop_pbo  
PROP_SE=prop_pbo_SE);  
by IMPUTATION_;  
run;
```

```
data trt_diff_640_pb01;  
set trt_diff_640_pbo;  

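### The multiple-imputation check draws a floor-heavy 0-7 score from a rounded, bounded normal regression and so understates clinical resolution among imputed subjects

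*SAP*

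**What the plan says.** SAP 10.3 (Method 2) imputes the Visit 3 GCS by regression on treatment, age stratum, baseline GCS and Visit 2 GCS. An MCMC step comes first if the missing pattern is not monotone. The text adds: "The imputed GCS data will be rounded to integers and bounded to 0 to 7 during imputation". The example code in SAP 20.2.2 does the same: "monotone regression (GCS_V3 = trt age1 age2 GCS_BASE GCS_V2", with the comment that "GCS_V2 and GCS_V3 are bounded to 0 to 7". A missing Visit 2 score is therefore rounded and bounded as well.

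The imputed score is converted to resolved only if it equals 0, in line with SAP 18.3: "Any non 0 sum means not reaching clinical resolution". SAP 2.5 sizes the trial "assuming 61% and 45% subjects with clinical resolution, respectively", so about half of all subjects are expected at the bottom of the scale.

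SAP 10.5 reuses the method for bacterial eradication. The code changes only the upper limit, in the comment that begins "Since bacterial eradication is a binary endpoint, the max bound for".

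For subjects with no post-baseline value, SAP 10 states that "the subject will be excluded from the primary analysis in mITT and sensitivity analysis in ITT for that efficacy assessment".

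**The concern.** A normal residual is symmetric around the fitted value. The Visit 3 score is expected to have a large spike at 0 and a tail to the right. A normal model matched to such data spreads its mass across 0, 1 and 2 and puts too little in the interval that rounds to 0. Too few imputed subjects are then counted as resolved, in both arms. The SAP does not say whether draws outside 0-7 are clipped to the limit or redrawn, and the answer changes the result. A subject with no Visit 2 score passes through two such draws.

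This matters because of the role of the analysis. LOCF drops subjects with no post-baseline value. Modified WOCF carries their baseline forward, which is always unresolved because an eligible eye scores at least 1 on both signs (SAP 10.1). Multiple imputation is the only planned analysis that estimates these subjects' outcome, and the only missing-at-random check on LOCF. As written, it is pulled toward the WOCF answer, so part of any agreement between the two would be an artefact.

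**Working it through.** **1. The plan's own figure.** Full enumeration of Fisher's exact test with 216 per arm and 61% vs 45% gives power of 89.9% at both 0.05 and 0.0499, matching the stated ~90%. The inputs 61%, 45% and 216 are used below.

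**2. Closed form.** Let p0 be the true share at 0 and w_k the shares of non-zero scores at k (assumed, because the documents give none). The matching normal has mean m = (1 - p0) * sum(k * w_k) and variance s^2 = (1 - p0) * sum(k^2 * w_k) - m^2. With F the normal CDF, the probability of an imputed 0 is:

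- clipped: F((0.5 - m)/s);
- redrawn after rounding: the same interval with the normal truncated to [-0.5, 7.5];
- redrawn before rounding: the same, truncated to [0, 7].

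Worked case, with non-zero scores 70/20/10% at 1/2/3:

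- SHP640: m = 0.39 * 1.4 = 0.546; s = sqrt(0.39 * 2.4 - 0.546^2) = 0.799; F(-0.058) = 0.48.
- Placebo: m = 0.55 * 1.4 = 0.770; s = sqrt(0.55 * 2.4 - 0.770^2) = 0.853; F(-0.317) = 0.38.

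| Non-zero scores (true 61%/45% at 0) | Clipped | Redrawn after rounding | Redrawn before rounding |
|---|---|---|---|
| 70/20/10% at 1/2/3 | 48%/38% | 42%/33% | 31%/24% |
| 40/30/20/10% at 1/2/3/4 | 40%/31% | 31%/24% | 21%/16% |
| all at 1 | 59%/46% | 58%/45% | 48%/38% |

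The last row is the exception: two of the three rules are then close to the truth. Moving 5% of the non-zero scores to 2 gives 56.8%/44.4% clipped, which already leaves SHP640 about 4 points short.

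**3. The SAP's regression, simulated.** There were 200,000 subjects per arm. Assumptions: latent visit correlation 0.3, 0.5 or 0.8; a light or heavy non-zero tail; baseline GCS 2-7; Visit 2 zeros 25%/15%; data missing completely at random. Resolution among imputed subjects (truth 61%/45%):

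| | Clipped | Redrawn after rounding | Redrawn before rounding |
|---|---|---|---|
| Visit 2 observed | 39-48%/30-37% | 26-44%/21-34% | 17-34%/13-27% |
| Visit 2 also missing | 38-46%/29-37% | 25-42%/20-34% | 16-32%/12-25% |

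**4. Effect on what is reported.** With missing share M, the fall in an arm rate is M * (true - imputed), and the fall in the difference is M * (16 - imputed difference). In the worked case at 5%, the SHP640 rate falls by 0.05 * (61 - 48) = 0.65 points and the difference by 0.05 * (16 - 10) = 0.3. Over all simulated cases:

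- 5% missing: arm rates fall 0.4-2.3 points, the difference 0.3-0.6;
- 10% missing: arm rates fall 0.8-4.5 points, the difference 0.6-1.3. A separate simulation with other score shapes, clipped or redrawn after rounding, took the difference from 16.0 to about 15.1-15.5.

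The standard error of the difference is sqrt(0.61 * 0.39/216 + 0.45 * 0.55/216) = 0.0474, or 4.7 points.

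**5. Missingness that rises with the Visit 2 score.** Take logit P(missing) = a + b * V2, with b = 0.5 or 1.0 and 5% missing overall. The true rate among missing subjects is then 14-55%/8-38%. The clipped rule is short by 7-21/3-13 points. Logistic imputation of the status is within 4 points.

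**6. Bacterial eradication.** The same normal, intercept only and bounded to 0-1, under all three rules: a true 45% becomes 46-48%, 61% becomes 55-59%, and 80% becomes 70-77%. The bias can go either way.

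**7. Code against text.** The second call, "proc mi data = impOne seed = 321 out = impFinal NIMPUTE = 1", reads the ten stacked datasets with no `BY _IMPUTATION_`, whereas SAP 10.3 describes ten separately imputed datasets. If the imputation index survives, the effect is negligible: pooled SE 0.0484 vs 0.0485 at 5% missing and 0.0517 vs 0.0520 at 20%. The documents do not settle whether it survives. If it were overwritten with a single value, the later steps would see one dataset of 10 * 216 = 2,160 per arm, with SE sqrt(0.4854/2160) = 0.0150.

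**The case against.** The strongest reply is that no decision changes. Inference rests on LOCF, and the shift in the difference is about a tenth of a standard error at 5% missing and in the conservative direction. That stands, and it is why the point is minor.

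Second, every size rests on assumed score shapes, correlations and missing shares. That also stands. The direction does not depend on them: it held under all three readings of the bounds for every shape tested with non-zero scores above 1. A score confined to 0 and 1 at Day 5 is implausible when baseline GCS is at least 2 and the SAP defines further endpoints for scores up to 1 and up to 2.

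Third, subjects doing badly are the ones likely to leave. Protocol 4.4 sends those who do not improve to Visit 5 evaluations before rescue, so missing completely at random is too kind a benchmark. Under missingness that depends on Visit 2 (5% overall), the fall in the difference was 0.2-0.4 points clipped and 0.2-0.5 redrawn after rounding. The harm is of similar size and in the same direction.

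Fourth, SAP 18.4 feeds assessments outside the visit windows into LOCF and WOCF, so the group with no post-baseline value may be small. That is fair, and the documents give no count. The imputation model, however, uses only the baseline, Visit 2 and Visit 3 scores, so a subject assessed only outside those windows is still imputed.

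Finally, the code is labelled as an example. The rounding and bounds are in the SAP text itself. Only the missing `BY` line is confined to the example.

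**Conclusion.** The concern holds and is minor. Following SAP 10.3 as written understates clinical resolution among imputed subjects in both arms, most plausibly by 10 points or more per imputed subject under missing completely at random. The arm rates and their confidence intervals from this analysis are therefore biased downward: by 0.4-2.3 points at 5% missing and 0.8-4.5 at 10%. The treatment difference shrinks by at most about 1.3 points at 10% missing, so the analysis cannot manufacture support for a positive result. The primary Fisher/LOCF test and its alpha are unaffected.

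Confidence is high for mechanism and direction. The sizes rest on the stated assumptions about Day 5 score shape, visit correlation and missing share. The bias nearly vanishes only when almost every unresolved subject scores 1 and draws are clipped or redrawn after rounding.

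**What to change.** - **Visit 3 clinical resolution:** impute the binary status directly by logistic regression on treatment, age stratum, baseline GCS and Visit 2 GCS. In the simulation this returns 61%/45% under missing completely at random, whether or not Visit 2 is observed, provided a missing Visit 2 score is filled as in the next item.
- **Missing Visit 2 GCS:** impute it first, by predictive mean matching or an ordinal model. Remove `ROUND`, `MIN` and `MAX` from both the MCMC and the regression steps. If MCMC still fills some Visit 2 scores, unrounded normal draws give 59-61%/44-45%; leaving them rounded and bounded gives 58-60%/42-45%.
- **Bacterial eradication:** use logistic imputation on treatment, age stratum, baseline GCS and Visit 2 eradication status, and say how a missing Visit 2 status is filled. No baseline culture term is needed, since every mITT subject is culture-positive at baseline (SAP 4.4). This model was not simulated.
- **Code:** add `BY _IMPUTATION_` to the second PROC MI so that it matches the text.

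The cost is a few lines of SAP text and example code, with no new data and no change to the primary analysis.
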